**Confidentiality Statement**

Data and information contained in this document are considered to constitute trade secrets and confidential commercial information, and the legal protections provided to such trade secrets and confidential information are hereby claimed under the provisions of applicable law. No part of this document may be publicly disclosed without the written consent of Philip Morris Products S.A.

Exclusion Criteria	Rationale	Screening Visit	Admission Visit
8. Subject has a positive serology test for HIV 1/2, Hepatitis B, or Hepatitis C.	Safety	X	
9. Subject has a positive alcohol breath test and/or a history of alcohol abuse that could interfere with the subject's participation in study.	Administrative	X	X
10. Subject has a positive urine drug test.	Administrative	X	X
11. Subject or one of their family members b is a current or former employee in the tobacco industry.	Administrative	X	
12. Subject or one of their family members b is an employee of the investigational site or of any other parties involved in the study.	Administrative	X	
13. Subject has participated in another clinical study within 3 months prior to the Screening Visit. The 3-month interval is calculated as the time between the first calendar day of the month that follows the last visit of the previous study and the first day of the present study.	Safety	X	
14. Subject has been previously screened or enrolled in this study.	Administrative	X	
15. For women only: subject is pregnant (does not have negative pregnancy tests at Screening Visit and at Admission Visit) or is breastfeeding.	Safety	X	X
16. For women of childbearing potential only c : subject does not agree to use an acceptable method of effective contraception. d	Safety	X	X
17. Use of estrogen-containing hormonal contraception or hormone replacement therapy	Effect	X	X

**Confidentiality Statement**

Data and information contained in this document are considered to constitute trade secrets and confidential commercial information, and the legal protections provided to such trade secrets and confidential information are hereby claimed under the provisions of applicable law. No part of this document may be publicly disclosed without the written consent of Philip Morris Products S.A.

b. As defined by FDA guidance on Human Subject Protection (21 CFR 50.3(l), (m), 50.24(a)(6), (a)(7)(v), b):  
"Family member" means among other things "parent", "spouse", "brothers, sisters, and spouses of brothers and sisters" and "any individual related by affinity...whose close association with the subject is equivalent of a family relationship"

c. Women who are not of childbearing potential meet at least one of the following criteria:  
Have undergone hysterectomy or bilateral tubal ligation,  
Have medically confirmed ovarian failure, or  
Are medically confirmed to be post-menopausal (cessation of regular menses for at least 12 consecutive months with no alternative pathological or physiological cause).

d. Intrauterine device, intrauterine system, barrier methods of contraception (condoms, occlusive caps) with spermicidal foam/gel/film/suppository, hormonal contraception containing progesterone only, vasectomized partner(s) from Screening until the end of the Safety Follow-up Period. Hormonal contraception with estrogen containing products is NOT allowed in this study.

## 6.3 Product Allocation and Blinding

### 6.3.1 Methods of Assigning Subjects to Treatment Sequences

On Day 1 subjects will use P3P 3. In the morning of Day 2, after confirmation that there are no safety concerns for each subject to continue in the study based on the Investigator's judgement, 18 subjects will be randomized to one of the following six sequences of the remaining product variants in order to cross-over the use of P3P 1, P3P 2 and P3P 4 following a 2 Latin squares design balanced for first order carryover effects among the 3 variants.

**Table 1 Treatment Sequences**

Sequence Number	Day 2	Day 3	Day 4
1	P3P 2	P3P 4	P3P 1
2	P3P 4	P3P 1	P3P 2
3	P3P 1	P3P 2	P3P 4
4	P3P 1	P3P 4	P3P 2
5	P3P 2	P3P 1	P3P 4
6	P3P 4	P3P 2	P3P 1

Details related to randomization procedures are provided in the randomization plan.

The enrolled subjects will be considered eligible for randomization if there are no safety concerns to continue in the study based on the Investigator's judgement.

Subjects discontinued before randomization will be replaced to reach 18 randomized subjects.

Subjects discontinued after randomization will not be replaced.

At least 8 subjects of each sex will be randomized to ensure each sex represents at least 40% of the randomized population and thus no more than 10 subjects of the same sex will be randomized.

#### Confidentiality Statement

Data and information contained in this document are considered to constitute trade secrets and confidential commercial information, and the legal protections provided to such trade secrets and confidential information are hereby claimed under the provisions of applicable law. No part of this document may be publicly disclosed without the written consent of Philip Morris Products S.A.

The treatment sequences will be assigned to the subjects through sequentially numbered opaque sealed envelopes (SNOSE method). The randomization letters will be generated through a dedicated SAS program as described in the randomization plan.

The randomization numbers will be assigned to the subjects eligible for randomization present at the clinical facility in the morning of Day 2 (they are confined since the evening of Day -1). The assignment should be performed according to the sequence of the subject numbers assigned during the screening visit.

If a sufficient number of subjects is already randomized to the study sequences, the supernumerous subjects will be discontinued prior to randomization.

The randomization scheme was generated by the CROSS' statistician who will be the only one having access to the live randomization codes prior to randomization together with the study monitor and the packaging provider, as detailed in the randomization plan. No one else of the study team, including study sponsor, CROSS and PI or the study subjects will be exposed to the live randomization codes prior to randomization.

### **6.3.2 Blinding**

This study will be conducted as an open label study with no blinding. However, in order to prevent selection bias, Study Team (Sponsor and CROSS Alliance), Investigator, the subjects and the investigational site will be blinded to the randomization sequences until they are assigned as described in Section 6.3.1 "Methods of Assigning Subjects to Treatment Sequences".

### **6.3.3 Compliance to Product Allocation**

Compliance will be ensured by strict distribution of the products (product by product) and collection of any used and unused investigational product by the designated site staff. The product accountability will be maintained by the investigational site staff and will include records for each product dispense and return.

## **7 DERIVED AND COMPUTED VARIABLES**

Mean change from baseline is the mean of all individual subjects' change from baseline values (baseline is defined in Section 4.1 "Definitions for Statistical Analysis"). Each individual change from baseline will be calculated by subtracting the individual subject's baseline value from the value at the timepoint. The individual subject's change from baseline values will be used to calculate the mean change from baseline.

Reported BMI will be calculated from the body weight and height using the following formula:

$$\text{BMI} \left[ \frac{\text{kg}}{\text{m}^2} \right] = \frac{10000 \times \text{Body Weight} [\text{kg}]}{(\text{Body Height} [\text{cm}])^2}$$

The QT interval corrected using Bazett's formula (QTcB) will be calculated as follows:

#### **Confidentiality Statement**

Philip Morris Products S.A.

Protocol P3P-PK-01-CH

Statistical Analysis Plan

Final v2.0 / 30 Apr 2018

Confidential

Page 25 of 90

$$\text{QTcB interval [msec]} = \frac{\text{QT interval [msec]}}{\sqrt{\frac{60}{\text{Heart Rate [beats/min]}}}}$$

The QT interval corrected using Fridericia's formula (QTcF) will be calculated as follows:

$$\text{QTcF interval [msec]} = \sqrt[3]{\frac{\text{QT interval [msec]}}{\frac{60}{\text{Heart Rate [beats/min]}}}}$$

Note that the BMI, QTcB, QTcF are available in the data collected in the CRF and will not be recalculated.

The geometric coefficient of variation (CV) will be calculated using the following formula:

$$CV = 100\sqrt{e^{var}-1}$$

where *var* is the variance from the log transformed data.

## 7.1 Pharmacokinetic Parameters

### 7.1.1 PK Analysis Materials

#### 7.1.1.1 Analysis Dataset

The final PK analysis is to be performed on the quality controlled and quality assured data, as provided by the bioanalytical laboratory, after database lock.

### 7.1.2 PK Parameters

For PK parameters, baseline is defined in Section 4.1 "Definitions for Statistical Analysis".

To minimize the carry-over effect in the nicotine plasma PK parameters due to limited washout periods, background-concentration correction will be applied to the concentration data for the fixed puffing regimen and *ad libitum* use. The baseline correction will be implemented by calculating the nicotine exposure parameters using adjusted concentration values. The plasma nicotine background-correction methodology will be confirmed following the conduct of an interim analysis as described in Section 13.1.3 "Interim Analysis Methods".

Nicotine PK parameters will be derived from both measured plasma nicotine concentrations, as well as the background-corrected plasma nicotine concentrations using noncompartmental analysis principles.

The actual blood sampling times post-exposure collected in the CRF will be used in the computation of the PK parameters, with the exception of pre-exposure sampling time which will be considered as time zero ( $T_0$  fix or  $T_0$  ad lib).

PK parameters for the fixed regimen use will be derived using the nicotine concentration assessed between  $T_0$  fix and the last available timepoint of the fixed regimen (4h±30min after product use). For the calculation of the AUC only, the window can be extended up to the pre-dose nicotine concentration before the *ad libitum* use.

PK parameters for the *ad libitum* use will be derived using the nicotine concentration assessed between  $T_0$  ad lib and the last available timepoint of *ad libitum* use (4h±30 min after first product use). For the calculation of the AUC only, the window can be extended up to the pre-dose nicotine concentration before the next fixed regimen use or, in the last period only, to the additional samples collected.

The following PK parameters will be calculated, as per protocol background-corrected PK endpoints, for the fixed (Table 2) and *ad libitum* (Table 3) regimens.

**Table 2 Background-corrected Fixed Regimen Nicotine Plasma PK Parameters**

Parameter	Definition
$cC_{max}$	Background-corrected maximum observed plasma concentration.

**Table 2 Background-corrected Fixed Regimen Nicotine Plasma PK Parameters**

Parameter	Definition
$c_{t_{\max}}$	Time of background-corrected maximum observed plasma concentration.
$cAUC_{fix(0-4h)}$	Background-corrected area under the concentration-time curve from start of product use ( $T_0_{fix}$ ) to 4 hours

**Table 3 Background-corrected Ad Libitum Regimen Nicotine Plasma PK Parameters**

Parameter	Definition
$cC_{peak}$	Background-corrected peak plasma nicotine concentration
$c_{t_{peak}}$	Time to peak plasma nicotine background-corrected concentration during ad libitum use, $c_{t_{peak}}$ will be reported as long as there is at least one quantifiable concentration post-exposure
$cAUC_{ad\ lib(0-4h)}$	Area under the concentration-time curve from start of product use ( $T_0_{ad\ lib}$ ) to 4 hours
$cC_{trough}$	Background-corrected trough plasma nicotine concentration from $T_0_{ad\ lib}$ to 1 hour
$cC_{average}^a$	Background-corrected average of plasma nicotine concentration from $T_0_{ad\ lib}$ to 1 hour

a  $cC_{average}$  is calculated by estimating the area under the concentration-time curve using background-corrected nicotine concentrations from the start of product use up to the last available concentration within 1 hour post product use, divided by the collection interval

Uncorrected PK parameters will also be presented, and the corresponding estimated PK parameters are described in Table 4, for the fixed regimens, and in Table 5, for the *ad libitum* regimens.

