**Table 5 Ad Libitum Regimen Nicotine Plasma PK Parameters (Uncorrected)**

Parameter	Definition
$C_{\text{peak}}$	Peak plasma nicotine concentration
$AUC_{\text{ad lib}(0-4h)}$	Area under the concentration-time curve from start of product use ( $T_0 \text{ ad lib}$ ) to 4 hours
$t_{\text{peak}}$	Time to peak plasma nicotine concentration during ad libitum use, $t_{\text{peak}}$ will be reported as long as there is at least one quantifiable concentration post-exposure
$C_{\text{trough}}$	Trough plasma nicotine concentration after from $T_0 \text{ ad lib}$ to 1 hour
$C_{\text{average}}^a$	Average of plasma nicotine concentration from $T_0 \text{ ad lib}$ to 1 hour

a  $C_{\text{average}}$  is calculated by estimating the area under the concentration-time curve from the start of product use up to the last available concentration within 1 hour post product use, divided by the collection interval

In addition,  $\lambda_z$ -related nicotine plasma PK parameters will be calculated following the last product use (Days 4 to 5), as shown in Table 6:

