## 12.6.2 Secondary Analyses

### 12.6.2.1 Pharmacokinetics

The same approach as for the Section 12.6.1 "Primary Analyses" will be conducted for the following background-corrected and uncorrected secondary PK parameters for *ad libitum* use:  $cC_{peak}$ ,  $cC_{trough}$ ,  $cC_{average}$ ,  $cAUC_{ad lib (0-4h)}$ ,  $ct_{peak}$ ,  $C_{peak}$ ,  $C_{trough}$ ,  $C_{average}$ ,  $AUC_{ad lib (0-4h)}$  and  $t_{peak}$ .

Background-corrected and uncorrected PK parameters for *ad libitum* use will be summarized by P3P variant.

The individual plasma nicotine concentrations over time and PK parameters will be summarized by P3P variant as detailed in section 12.1.3 "Descriptive Statistics" and will be presented by sex as described in Section 12.1.1 "Stratified Presentation" (Tables 15.2.3.8 and 15.2.3.8.1 for background-corrected concentrations, Tables 15.2.3.9 and 15.2.3.9.1 for uncorrected concentrations, Tables 15.2.3.10 and 15.2.3.10.1 for background-corrected PK parameters, Tables 15.2.3.11 and 15.2.3.11.1 for uncorrected PK parameters).

The individual uncorrected and background-corrected plasma nicotine concentrations and actual sampling times will be listed (Listing 15.3.3.3).

The individual uncorrected and background-corrected PK parameters will be listed (Listing 15.3.3.4).

The individual plasma nicotine concentrations over time will be plotted up to 4 hours by P3P variant in a linear and semi-logarithmic scale (Figures 15.1.3.13 and 15.1.3.14 for background-corrected concentrations, Figures 15.1.3.15 and 15.1.3.16 for uncorrected concentrations).

The geometric mean plasma nicotine concentrations over time will be plotted up to 4 hours by P3P variant and their 95% CI (Figures 15.1.3.17 and 15.1.3.18 for background-corrected concentrations, Figures 15.1.3.19 and 15.1.3.20 for uncorrected concentrations).

Boxplots of  $cC_{peak}$ ,  $cC_{trough}$ ,  $cC_{average}$ ,  $cAUC_{ad lib (0-4h)}$ ,  $C_{peak}$ ,  $C_{trough}$ ,  $C_{average}$  and  $AUC_{ad lib (0-4h)}$  by P3P variant will be presented (Figures 15.1.3.21-28).

Geometric least square means and ratios will be presented for the analysis of  $cC_{peak}$ ,  $cC_{trough}$ ,  $cC_{average}$ ,  $cAUC_{ad lib (0-4h)}$ ,  $C_{peak}$ ,  $C_{trough}$ ,  $C_{average}$  and  $AUC_{ad lib (0-4h)}$  together with 95% confidence interval by sex and overall for the following effects of interest (Table 15.2.3.12, Table 15.2.3.12.1, Table 15.2.3.13 and Table 15.2.3.13.1):

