#### **13.1.3.1 Primary PK Analysis Methodology (NCA-based method)**

The nicotine terminal elimination rate constant  $\lambda_z$  (and  $t_{1/2z}$ ) will be estimated as described in Section 7.1.2.3 "Criteria for Calculating the Apparent Terminal Elimination Half-Life". For the purposes of background-correction of the plasma concentrations post-baseline the following formula will be applied:  $cC_t = C_t - C_0 \cdot e^{-\lambda_z \cdot t}$ . Where  $cC_t$  is the corrected concentration at each time point,  $C_t$  is the concentration at each time point,  $C_0$  is the pre-use baseline concentration,  $\lambda_z$  is the terminal elimination rate constant and  $t$  is the actual time.

If the predicted  $cC_t$  is  $< 0.2$  ng/mL (the bioanalytical LOQ threshold), this value will be used for the estimation of the background-corrected PK parameter (NCA analysis) only if the corresponding  $C_t$  is above LOQ, and the predicted  $cC_t$  will be imputed by zero if

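### The ad libitum trough window does not exclude the pre-use sample; if that sample counts, the corrected trough is 0 in every profile and its planned log-scale analysis cannot be run

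*SAP*

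**What the plan says.** - **Window.** SAP Table 3 gives cCtrough as "Background-corrected trough plasma nicotine concentration from" T0 ad lib to 1 hour. Table 5 gives the uncorrected counterpart as "Trough plasma nicotine concentration after from" T0 ad lib to 1 hour, where the double preposition leaves the start of the window unclear.
- **Pre-use sample.** SAP 7.1.2 uses actual sampling times "with the exception of pre-exposure sampling time which will be considered as time zero", that is, T0 fix or T0 ad lib. Ad libitum parameters "will be derived using the nicotine concentration assessed between" T0 ad lib and the last available time point.
- **Correction.** SAP 13.1.3.1 sets cC_t = C_t − C_0·exp(−λz·t), where C_0 "is the pre-use baseline concentration". A corrected value "will be imputed by zero if" negative.
- **Missing and BLOQ values.** SAP 12.1.5 treats a missing or BLOQ baseline as 0 when PK parameters are derived.
- **Analysis.** SAP 12.6.2.1 applies the approach of 12.6.1, a mixed model on log-transformed parameters, to cCtrough and Ctrough. "Geometric least square means and ratios will be presented for the analysis of" a list of parameters that includes both, by sex and overall, and a sensitivity model follows.

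SAP 7.1.2.1 and 7.1.2.2 give calculation rules for Cmax, tmax, Cpeak, tpeak and AUC. There is no such rule for the trough, and no rule for zeros entering a log model.

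**The concern.** The sample used to correct each profile is also the first point of the window over which the trough is sought. Subtracting a sample from itself leaves zero, and the negative-value rule means that nothing can fall below zero. A minimum over that window therefore carries no information about the variant, and it has no logarithm.

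At stake is a listed secondary endpoint. In corrected form it would have no model estimate, geometric mean or ratio. In uncorrected form it could describe nicotine left over from earlier use, which the correction exists to remove. Whether this happens depends on a choice that the SAP leaves to whoever programs the derivation.

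**Working it through.** The plan states no figure for this point. The sample size is empirical: 6 sequences × 3 = 18 subjects.

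**1. Points in the window.** With the pre-use sample placed at T0, the ad libitum window holds six points: 0, 10, 20, 30 and 40 minutes and 1 hour (SAP 6.1 and 7.1.2).

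**2. Corrected value at T0.** cC_0 = C_0 − C_0·exp(−λz·0) = C_0 − C_0 = 0, for any C_0 and any λz. For example, C_0 = 3 ng/mL gives 3 − 3 × 1 = 0. A missing or BLOQ baseline gives 0 − 0 = 0. Using the true time of −15 minutes would not help. With the 17 h half-life in Protocol 4.2, λz = ln 2/17 = 0.0408 per hour and exp(0.0408 × 0.25) = 1.0102. So cC = −0.0102·C_0, which is set to 0.

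**3. Minimum over the window.** No corrected value is below 0 and one is exactly 0, so the minimum is 0 in every profile corrected this way. The maximum number is 18 × 4 = 72.

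**4. Effect on the outputs.** log(0) is undefined, so no cCtrough value can enter the model. The geometric CV in SAP 7, 100·√(e^var − 1), needs the variance of the logs and fails too. Arithmetic mean, SD, median and quartiles can be computed (all 0), and a boxplot can be drawn, flat at zero.

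**5. Uncorrected Ctrough on the same reading.** If concentrations rise after the start of use, the minimum is the pre-use value. It is 0 where the baseline is BLOQ or missing.

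**6. Simulation of the SAP rules.** The documents give no concentrations for this product, so these ranges are assumptions: half-life 2 to 17 h, baseline 0 to 5 ng/mL, median rise per sampling interval 0.3 or 2 ng/mL, assay error 8%. The LLOQ is 0.2 ng/mL, from SAP 13.1.3.1. There were 4,000 profiles in each of 4 × 3 × 2 × 2 = 48 scenarios (half-lives, baseline bands, rises, and pre-use time taken as 0 or −15 minutes).

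| Quantity | Result |
|---|---|
| cCtrough = 0, pre-use sample included | 100% in every scenario |
| cCtrough = 0, samples from 10 min to 1 h only | 0% to 25.7% |
| Same, rise of 2 ng/mL per interval | at most 2.0% |
| Uncorrected Ctrough = 0, pre-use included, baseline 0 to 0.5 ng/mL | 39% to 42% |
| Same, baseline above 0.5 ng/mL | 0% |

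The zeros that remain after excluding the pre-use sample come mainly from small rises on a high baseline. With C_0 = 3 ng/mL and a 17 h half-life, the amount subtracted at 10 minutes is 3 × exp(−0.0408/6) = 2.98 ng/mL. Any measured value below that becomes 0.

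**The case against.** The best defence is that the SAP does not mean the pre-use sample to count:

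- The abbreviation lists in both documents place Ctrough within the ad libitum use period, whereas the pre-use sample is drawn 15 ± 5 minutes before it.
- The formula is introduced with a limit: "For the purposes of background-correction of the plasma concentrations post-baseline the following formula will be applied". On that wording no corrected value is defined at baseline.
- The stray word in Table 5 may point the same way.
- Trough is nowhere defined as the window minimum.

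A programmer could therefore use only post-start samples without breaching the SAP. This stands as evidence of intent, but it does not settle the text. No sentence excludes the T0 sample, and 7.1.2 puts it at the start of the window. cCaverage and cAUC also begin at the start of use and need a value there. Reading trough as the minimum is the natural counterpart of Cpeak, which the abbreviation list gives as the highest concentration in the same period.

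It is also fair to say that the consequence is limited. This is a pilot with no hypothesis and no claims based on individual intervals, and the fault would probably surface at programming.

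A reader might infer more than the documents support:

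- **That no output for cCtrough could be produced.** SAP 12.1.3 presents geometric statistics in addition to arithmetic ones, so only the log-based results fail.
- **That 72 values are certain to be lost.** Discontinued subjects are not replaced after randomization, subjects without λz have no corrected profile under this formula, and the population-PK fallback works by simulation.
- **That uncorrected Ctrough always measures carry-over.** That requires concentrations to rise after the start of use, which is plausible but assumed.

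**Conclusion.** Wrong as written, with moderate confidence. Following Tables 3 and 5 and SAP 7.1.2 literally, and taking trough as the lowest value in the window, cCtrough is 0 in every profile corrected with the SAP formula, under either an NCA or a compartmental λz. Its log-scale model, sensitivity model, geometric mean and CV, and three variant ratios then do not exist. On the same reading, uncorrected Ctrough equals the pre-use level whenever concentrations rise, and is 0 where the baseline is BLOQ or missing.

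The result at T0 is algebraic and does not depend on the simulation. Confidence is moderate because other wording suggests that a post-start trough was intended. The primary endpoints, cCpeak, cCaverage and cAUC are unaffected.

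**What to change.** In Tables 3 and 5, define Ctrough and cCtrough as the lowest concentration among the post-start ad libitum samples T1 to T5 (10 minutes to 1 hour), excluding the pre-use sample. This agrees with the abbreviation list.

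In SAP 12.6.2.1, add a rule for zeros. Report the number of zero values per variant. If any occur, give the variant comparisons for cCtrough as median differences with Hodges-Lehmann 95% CIs, the method already planned for tpeak. Present the log model on positive values as supportive only. Zeros should not simply be dropped: that removes the lowest values selectively. If the 1 mg variant has more of them, its geometric mean rises and the P3P 2 to P3P 3 ratio is pulled down.

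The cost is one definition in two tables, one rule and a small addition to the outputs, with no new data. There are two downsides. With rising profiles the trough will often be the 10-minute sample, and the Hodges-Lehmann comparison does not adjust for sequence or study day as the mixed model does.
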